**Comparing Fascia Iliaca Compartment Block with Pericapsular Nerve
Group Block for Hip Fracture Pain Control before Operation**

Study Protocol with SAP (statistical analysis plan)

Date: 12/04/2019

Background

Hip fracture is a global health care concern. It is estimated that the number of hip fractures globally was 1.6 million in 2000¹, and will be increased to 6.25 million by 2050². Timely surgery is the mainstay of treatment for hip fractures³. Before operation, pain management for hip fracture is a clinical challenge. The fracture-induced pain is so intense that medical treatment with acetaminophen, non-steroid anti-inflammatory drugs (NSAIDs) or opioids may not provide adequate analgesia. Furthermore, opioid analgesia is limited by side effects such as nausea, vomiting, dizziness, sedation, and respiratory depression. On the contrary, peripheral nerve block provides better pain control for hip fracture than opioids^{4,5}. Fascia iliaca compartment block (FIC block), for example, has been repeatedly shown to be superior to opioids for pain control for hip fracture^{5,6}. Recently, a novel peripheral nerve block technique, the “pericapsular nerve group block (PENG block)”⁷, has been developed for hip fracture pain control. PENG block is considered to provide better coverage of articular branches from the obturator nerve than FIC block, and thus might be superior to FIC block in hip fracture pain control. However, there is no study comparing the analgesic effect for hip fracture pain between the FIC block and PENG block.

Aim

The aim of this study is to compare the analgesic effect of FIC block and PENG block in hip fracture pain control.

Methods

This will be a randomized, assessor and participant-blinded study. Adult patients (aged 20 years or older) scheduled for surgical treatment for hip fracture with American Society of Anesthesiologists (ASA) physical status I-III will be assessed for eligibility to participate the study. The exclusion criteria includes: allergy to local anesthetics, pregnancy, inability to understand and use the numerical rating scale (NRS 0-10, 0: no pain, 10: worst pain imaginable) after instruction, chronic use of opioids, coagulopathy, neuropathy or severe diabetic mellitus. If the patients give his /her informed consents, his/her baseline demographic data (gender, age, height, and body weight) and types of hip fracture will be recorded. Participants will be randomly allocated into either FIC block or PENG block by using the website RESEARCH RANDOMIZER (<https://www.randomizer.org>). One of the two anesthesiologists experienced in performed the FIC and PENG blocks will perform the nerve blocks. Only the anesthesiologist performing the nerve block and his assistant will be aware of which nerve block the participant received immediately

before performing nerve block by opening a sealed envelope. The assessors, in-charge anesthesiologists and nurse anesthetists, operation room personnel, surgeons and study participants will be all blinded to the randomization. The participants are unlikely to know which nerve block they receive because the needle insertion sites and needle trajectories of these two nerve blocks are quite close to each other.

On arrival of the operating theater, all participants will be sent to the nerve block area, where continuous electrocardiogram (ECG), pulse oximetry, and non-invasive intermittent blood pressure monitoring will be applied and an intravenous line will be established. Before any intervention, pain at rest and during the fractured lower limb being passively internal rotated in extension to neutral position from its usual externally rotated deformity by assessors will be assessed using NRS. If the participant cannot tolerate passive internal rotation of his/her fractured limb due to pain, impossibility to perform the test will be recorded as well as the worst NRS score during these attempts. The same assessment will be performed every 10 mins for until 30 mins after completion of the nerve block. Then the patient will be sent to the operation room, where spinal anesthesia will be performed for the surgery.

Procedures of the nerve blocks

A supra-inguinal FIC block will be performed in the way as described previously⁸.⁹ A linear ultrasound transducer (6-15 MHz, SonoSite, M-Turbo, USA) is placed in a sagittal plane to identify the anterior superior iliac spine (ASIS). By sliding the transducer medially, the fascia iliaca and abdominal internal oblique, satorius, and iliopsoas muscles are identified. After identifying the "bow-tie sign", a 23-gauge needle (7mm, Nipro, Japan) is inserted in plane from caudal to cephalad until the needle tip penetrate the fascia iliaca. After negative aspiration, 0.35% ropivacaine 30mL with 1:400,000 epinephrine will be injected to separate the fascia iliaca and the iliacus muscle.

The PENG block will be performed as previously described⁷. A curvilinear ultrasound transducer (2-5 MHz, SonoSite, M-Turbo, USA) is initially place on the anterior inferior iliac spine (AIIS) and then aligned to the iliopubic eminence by rotating around 45 degree. In this view, the iliopubic eminence, iliopsoas muscle and tendon, pectineus muscle, femoral artery and vein will be identified. A 23-gauge needle (7mm, Nipro, Japan) is inserted in plane from lateral to medial until the needle tip in the musculofascial plane between the psoas tendon anteriorly and the pubic ramus posteriorly. After negative aspiration, 0.35% ropivacaine 20mL with 1:400,000 epinephrine will be injected.

Outcome measurements

The primary outcome of this study is the pain measurement at rest and during the fractured limb being passively internally rotated 30 mins after nerve block. The secondary outcomes includes the pain measurement during positioning for spinal anesthesia (from supine to lateral decubitus with flexion of the healthy hip), pain measurement at 6, 12, and 24 hours after operation, the time spending for performing spinal anesthesia (defined as starting of positioning maneuver to removal of spinal needle), quality of position for spinal anesthesia (characterized as unsatisfied, satisfied, good, and excellent by the anesthesiologists performing the spinal anesthesia), the time interval between the end of operation and pain first perceived by the patient, the time interval between the end of operation and the first request for rescue analgesics, total consumption of rescue analgesics within 24 hours after the operation, the time interval between the end of operation and the first time the patient can ambulate with assistance after operation, the time spending for nerve block (defined as from contact of skin by the ultrasound transducer to removal of the needle), and satisfaction of the patient regarding preoperative analgesia from nerve block (very good, good, adequate, poor, very poor) inquired on the 1st postoperative day.

Statistics

Based on a previous study, the standard deviation of pain score after FIC block was 2.4¹⁰. Assuming the minimal clinically important difference in NRS score is 1.5, 44 patients in each group are required to achieve a power of 80% and a level of significance of 5% (two sided). One hundred eligible patients (50 patients in each group) will be enrolled in the study after informed consents are obtained. The data of normal distribution will be analyzed with independent *t*-test, otherwise Mann-Whitney U test will be used for analyses. Categorical data will be analyzed using χ^2 test or Fisher's exact test. $P < 0.05$ will be considered statistically significant.

There is no conflict of interest.

Reference

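### Fracture type and pre-block pain score are recorded at baseline but not used in the analysis: a small, optional gain in precision is missed

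*Combined protocol and SAP*

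**What the plan says.** In Methods, once consent is given, "types of hip fracture will be recorded" along with sex, age, height and weight. No categories are defined. The next sentence describes allocation: "Participants will be randomly allocated into either FIC block or PENG block by using the website RESEARCH RANDOMIZER". No stratification factor is named. That fracture type is noted before allocation is inferred from the order of the text.

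Methods also has pain scored at rest and on passive internal rotation before any intervention. If the movement cannot be tolerated, the worst score during the attempts is kept, so a baseline movement score should exist for those patients too. The same two scores at 30 minutes after the block are the primary outcome (Outcome measurements).

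In Statistics, normally distributed data go to an independent t-test; "otherwise Mann-Whitney U test will be used for analyses". For the rest, "Categorical data will be analyzed using" a chi-square or Fisher's exact test. No covariate, stratified or subgroup analysis is planned, and neither fracture type nor pre-block NRS is mentioned there.

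**The concern.** Two baseline variables that may predict the outcome are collected and then left out. Pre-block NRS is the same measure as the outcome, taken on the same patient about half an hour or more earlier. Fracture type is a plausible second candidate. The Background expects PENG block to give "better coverage of articular branches from the obturator nerve than FIC block", an anatomical argument, and the outcome is provoked by moving the fractured limb.

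An unadjusted test leaves any variance these variables explain in the error term. With 50 per arm, a chance difference between arms in either variable can also move the estimate in the one trial that is run. If such a difference appeared, an adjustment chosen after seeing it would carry less weight than one written down now.

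**Working it through.** **Inputs.** From Statistics: SD 2.4, target difference 1.5 NRS, two-sided 5%, 80% power, 44 required and 50 enrolled per arm. By assumption, because the documents are silent: the share of 30-minute NRS variance explained (R²), two fracture types, their frequency, and the NRS gap between them.

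**1. The plan's own figure.** The normal formula n = 2 × [2.4 × (1.96 + 0.84) / 1.5]² gives 40.2, so 41 per arm. The exact t-test calculation gives 42. Dividing 42 by the Mann-Whitney efficiency 3/π gives 43.98, so 44. The plan does not say that this was the route, but its 44 is reasonable.

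**2. Unadjusted position.** SE of the difference = 2.4 × √(2/50) = 0.480. Power for 1.5 points at 50 per arm is 87.2% by t-test and about 85.6% by Mann-Whitney. At 44 per arm the t-test has 82.6%.

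**3. Fracture type alone.** For two equally common types, R² = 0.25 × gap² / 2.4². Estimating one extra term multiplies the SE by about √(97/96) = 1.005. Net SE factor = √(1 − R²) × 1.005.

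| Gap (NRS) | R² | Net SE factor | Power before the 1.005 cost | Power after it |
|---|---|---|---|---|
| 0.5 | 0.011 | 0.9997 | 87.5% | 87.2% |
| 1.0 | 0.043 | 0.983 | 88.6% | 88.2% |
| 1.5 | 0.098 | 0.955 | 90.3% | 90.0% |

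A 0.5-point gap gives no net gain, and a 1.0-point gap takes about 1.7% off the SE. An equal split is the most favourable case: at 30% prevalence the R² for a 1.0-point gap is 0.037. With four types (three terms, factor √(97/94) = 1.016), R² = 0.043 leaves 0.994 and R² = 0.011 gives 1.010, a net loss.

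**4. Baseline NRS, then fracture type.** A baseline-outcome correlation of 0.32 to 0.50 corresponds to R² of 0.10 to 0.25.

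| Total R² | SE | Power at 50 per arm |
|---|---|---|
| 0.10 (baseline NRS) | 0.455 | 90.3% |
| 0.11 (adding 0.01) | 0.453 | 90.7% |
| 0.15 (adding 0.05) | 0.443 | 91.9% |
| 0.25 (baseline NRS) | 0.416 | 94.7% |
| 0.26 (adding 0.01) | 0.413 | 94.9% |
| 0.30 (adding 0.05) | 0.402 | 95.9% |

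Baseline NRS adds about 3 to 7.5 points of power to the 87.2%. Fracture type then adds about 0.3 to 1.5 points. Charging about 0.5% on the SE for each term reduces that second increment to about 0 to 1.3 points.

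**5. Chance imbalance in fracture type.** At 50% prevalence the difference in share between arms has SD √(2 × 0.25 / 50) = 0.10. The probability of a difference of 10 or more percentage points is 0.37, and of 20 or more 0.057. A 20-point imbalance shifts the estimate by 0.20 × gap: 0.2 NRS for a 1.0-point gap and 0.3 for a 1.5-point gap, against an SE of 0.480.

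**The case against.** The strongest reply is that nothing here is broken. The unadjusted comparison of randomised arms is valid, its type I error already allows for chance imbalance, and 50 per arm gives more than the intended power. That stands. So does the point that every gain above rests on an assumed R². The documents give no fracture-type distribution, define no categories, and do not say that type predicts the 30-minute NRS. Any effect of fracture type on initial pain would also be largely carried by baseline NRS, so its own increment could be nil.

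Several stronger readings are tempting, but the documents do not support them.

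- *Adjustment is a free gain.* It costs a degree of freedom per term, needs a category definition that the protocol lacks, and moves the primary analysis away from the planned rank-test fallback.
- *Allocation should have been stratified by fracture type.* Nothing in the documents shows that an imbalance large enough to matter is likely; 20 points or more has a probability of about 0.06.
- *The anatomical rationale makes fracture site the plan's own predictor.* The Background speaks of nerve coverage and does not mention fracture site. If site changes how well a block works, that is effect modification, which a main-effect covariate does not address.
- *The same covariate belongs in the rescue-analgesic and ambulation analyses.* The plan names no model for those outcomes in which a covariate could sit.

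What survives is narrower: for the primary outcome, usable baseline data are already in hand and a linear model would use them.

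**Conclusion.** The omission is real and its consequence is small. The planned test is valid and adequately powered, at about 87% for 1.5 points with SD 2.4 and 50 per arm. A prespecified ANCOVA would probably raise power to about 90 to 95%, provided that baseline NRS explains 10 to 25% of the variance. Fracture type is a minor addition: it falls to no net gain at an R² of about 0.01 and becomes a slight loss below that or with many categories. Its case rests as much on settling the adjustment in advance as on precision. This is an optional improvement; the conclusions of the trial do not depend on it.

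**What to change.** In Statistics, prespecify a linear model (ANCOVA) for the 30-minute NRS with three terms: treatment, the matching baseline NRS (rest for the rest outcome, movement for the movement outcome), and fracture type in two categories fixed before unblinding, for example intracapsular versus extracapsular. Keep the planned t-test or Mann-Whitney test as a sensitivity analysis.

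The cost is a rewritten analysis paragraph and a category definition, with no new data, visits or patients. The statistical price is one degree of freedom per term, about 0.5% on the SE each (√(97/95) = 1.010 for both), and the rank test is no longer a route to the primary result. If only one covariate is to be used, baseline NRS is the one to keep.

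### Operator is not described as recorded, fixed before allocation is revealed, or used in the analysis: a possible small loss of precision, most relevant to block time, and not a bias

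*Combined protocol and SAP*

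**What the plan says.** In the Methods, two anesthesiologists share the work: "One of the two anesthesiologists experienced in performed the FIC and PENG blocks will perform the nerve blocks". Allocation is described in one sentence, "Participants will be randomly allocated into either FIC block or PENG block by using the website RESEARCH RANDOMIZER", and the person doing the block learns the arm just "before performing nerve block by opening a sealed envelope". No stratum, block structure or rule for choosing the operator is described. The baseline items listed for recording cover demographics and fracture type; operator is not among them.

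Under Outcome measurements, the primary outcome is "pain measurement at rest and during the fractured limb being passively internally rotated 30 mins after nerve block". One of the secondary outcomes is "the time spending for nerve block (defined as from contact of skin by the ultrasound transducer to removal of the needle".

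The Statistics section takes 1.5 NRS points as the smallest difference that matters to patients, and from this it concludes that "44 patients in each group are required to achieve a power of 80% and a level of significance of 5% (two sided". The planned enrolment is somewhat larger than that figure: "One hundred eligible patients (50 patients in each group) will be enrolled in the study". The planned tests are a t-test or Mann-Whitney U test for continuous data and a chi-square or Fisher's exact test for categorical data. No covariate or stratified analysis is mentioned.

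**The concern.** Both interventions are ultrasound-guided injections done by hand, with different probes, views and needle targets (Procedures of the nerve blocks). Who does the block may therefore affect the result. If the two operators differ on average and operator is left out of the analysis, their difference becomes part of the residual variance. By chance, one arm may also receive more of one operator's work than the other. These are two views of the same variance, not two separate harms.

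Block time is the most exposed outcome because it measures the operator's own activity. There is also a practical stake: if operator is not recorded at the time, neither adjustment nor a simple display by operator may be possible later.

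**Working it through.** **Inputs from the Statistics section:** SD 2.4 (from an earlier study, after FIC block), target difference 1.5, two-sided 5%, power 80%, 44 per group required, 50 per group enrolled.

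**Assumptions, because the documents give no figures:** the operators share patients equally (p = 0.5); their means differ by d, the same in both arms; d is 0.5 to 2 NRS points for pain, and 0.5 to 2 within-operator SDs for block time.

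1. *The plan's own sample size.* The normal formula gives n = 2 × [2.4 × (1.960 + 0.842) / 1.5]² = 40.2, so 41 per group. The exact t-test calculation gives 41.2, so 42. Dividing 42 by the Mann-Whitney efficiency of 0.955 gives 43.98, so 44. The stated 44 is thus reproduced on the rank-test route and is within 2 of the t-test figure. At 50 per group, t-test power is 87.2%.

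2. *Chance imbalance.* The SD of the between-arm difference in operator share is √(2 × 0.5 × 0.5 / 50) = 0.10, with a 95% range of about ±0.20. The shift in the arm difference has SD 0.10 × d. For d = 1 the 95% range is 1.96 × 0.10 × 1 = ±0.20 NRS points; for d = 0.5 it is ±0.10 and for d = 2 it is ±0.39. The target is 1.5.

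3. *Variance of the primary score.* Operator adds p(1 − p)d² = 0.25d². If this comes on top of 2.4² = 5.76, then for d = 1 the share explained is 0.25 / (5.76 + 0.25) = 4.2%. Adjustment multiplies the interval width by √(1 − 0.042) = 0.979, so about 2% narrower.

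4. *Power at 50 per group, unadjusted, operator variance added to SD 2.4:*

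| d (NRS points) | SD | Power |
|---|---|---|
| 0 | 2.40 | 87.2% |
| 0.5 | 2.41 | 86.8% |
| 1 | 2.45 | 85.8% |
| 1.5 | 2.51 | 84.0% |
| 2 | 2.60 | 81.5% |

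If SD 2.4 already contains the operator variance, adjusting raises power from 87.2% to 88.6% at d = 1 and to 92.6% at d = 2.

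5. *Validity.* In simulated trials with operator assigned independently of arm, the unadjusted t-test rejected a true null in 5.0%, 5.0% and 5.1% of trials for d = 1, 2 and 4.

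6. *Block time, in within-operator SD units.* The variance is inflated by the factor 1 + d²/4, and adjustment narrows the interval by 1 − 1/√(1 + d²/4):

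| d (within-operator SDs) | Variance inflation | Interval narrower by |
|---|---|---|
| 0.5 | 6% | 3% |
| 1 | 25% | 11% |
| 2 | 100% | 29% |

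7. *What a by-operator comparison can show.* With about 25 patients per cell, each operator's arm difference has SE 2.4 × √(2/25) = 0.68. The difference between the two has SE √2 × 0.68 = 0.96, so its 95% interval is about ±1.96 × 0.96 = ±1.9 NRS points, wider than the 1.5-point target.

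**The case against.** The strongest reply is that this hardly matters for the question the trial asks. Both operators perform both blocks, so operator is not tied to arm by design. Randomisation makes any imbalance random, and the unadjusted standard error already includes it. At 50 per group and SD 2.4 the standard error is 2.4 × √(2/50) = 0.48; a 2% change in interval width is trivial beside that. Block time is one of several secondary outcomes and lies outside the stated aim of comparing analgesia. All of this stands, and it limits the point to an inexpensive improvement.

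Four stronger readings are tempting, but the documents do not support them:

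- *The arm comparison is biased.* Nothing says that the operator is chosen by allocation. The Methods suggest that whoever opens the envelope is already the operator, although this is not stated as a rule.
- *The operators are less skilled at PENG.* The Background calls the technique novel in general; the Methods describe both operators as experienced in both blocks. No operator difference is given.
- *There is one allocation list common to both operators.* The number of lists and any blocking are not stated. The supportable statement is that use of operator in the randomisation is not described.
- *Adding operator to the model would show whether the result holds for both operators.* A single operator term does not model a difference in the arm effect between operators, and step 7 shows that such a difference would be estimated too imprecisely to settle the matter.

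**Conclusion.** The omission is real and minor. It can cost some precision; it does not threaten the validity of the planned tests, provided that the operator is not chosen in the light of the allocation.

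For the primary NRS the loss is small across the assumed range: power stays above 80% at 50 per group even with a 2-point gap between operators. For block time the gain from adjustment could be worthwhile, but its size depends wholly on an operator gap that the documents do not give, and at half a within-operator SD it is slight. All these figures assume an equal operator split and an operator difference that is the same in both arms. SD 2.4 may already include some operator variation.

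**What to change.** - Determine who will perform the block before the envelope is opened, and state this in the Methods.
- Record operator on the case report form.
- Prespecify operator as a term in the analysis of block time and of the 30-minute NRS: a linear model with arm and operator, or the van Elteren test stratified by operator if the rank-based route is taken.
- Show arm results by operator descriptively, without claiming that they establish consistency.

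I would not add a separate permuted-block envelope series for each operator. The operator opens the envelopes and sees past allocations, so a personal blocked series would make later allocations easier to predict. Recording operator and adjusting for it needs no such series.

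The cost is one data field and one model degree of freedom, with no extra patients. If the two operators perform alike, there is little gain.

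### Does the primary rotation comparison lack a rule for participants whose limb cannot be rotated at 30 minutes because of pain?

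*Combined protocol and SAP*

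**What the plan says.** The Methods section has pain scored on the 0–10 NRS at rest and during passive internal rotation before the block. For a rotation that pain prevents, "impossibility to perform the test will be recorded as well as the worst NRS score during these attempts". It continues: "The same assessment will be performed every 10 mins for until 30 mins after completion of the nerve block". The provision for failed tests therefore applies at 30 minutes too.

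Under Outcome measurements, the primary outcome is "the pain measurement at rest and during the fractured limb being passively internally rotated 30 mins after nerve block". A failed rotation is not mentioned there, and inability to rotate is not among the secondary outcomes.

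The Statistics section is generic. Normally distributed data get an independent *t*-test; "otherwise Mann-Whitney U test will be used for analyses". "Categorical data will be analyzed using" a χ² or Fisher's exact test, with no variable named. There is no separate rule for missing data or exclusions. The sample size rests on an SD of 2.4 and a 1.5-point difference.

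**The concern.** One failed test produces two data items, a flag and a score, and the plan does not say what either is for in the analysis. Three treatments are conceivable: analyse the worst score, rank the participant below everyone who completed, or drop the participant as not tested. If the choice were left until the data had been seen, the most favourable result could be picked, and blinded scoring would not prevent that.

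A second worry concerns meaning. Someone who stops at NRS 5 has not endured the same stimulus as someone who completes at NRS 6, yet counts as having less pain. If failures are common and more frequent in one arm, the NRS difference could understate the difference in pain on full rotation. A reader setting it against the protocol's 1.5 points would not see this. Only the rotation part of the primary outcome is affected; pain at rest is not.

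**Working it through.** **1. The plan's own figure.** Inputs from the Statistics section: difference 1.5, SD 2.4, power 80%, two-sided 5%.

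- Normal approximation: n = 2(1.960 + 0.842)² × 2.4² / 1.5² = 40.2, so 41 per group.
- Exact *t*-test: 41.17, so 42.
- Divided by the Mann-Whitney efficiency of 0.955: 41.17 / 0.955 = 43.1, so 44, as stated.

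At the 50 per group to be enrolled, *t*-test power is about 87%. The sample size is not in question.

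**2. The sections side by side.** Methods defines how rotation pain is measured, including what is scored when rotation fails, and carries that measurement to 30 minutes. Outcome measurements then takes the 30-minute rotation pain measurement as primary. A participant who could not complete therefore has a primary value, the worst NRS during the attempts. No sentence allows it to be removed or replaced by a worst rank. The flag is a yes/no variable, and the categorical-data sentence is broad enough to cover it.

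**3. Size if tolerance varies between people.** Assumed, not in the documents: full-rotation means 4.0 v 5.5, SD 2.4, 50 per arm. Scores are rounded and clipped to 0–10. A test fails if pain exceeds a personal tolerance T and is then scored T + 1. T is a uniform integer on 8–10 (rare failures), 6–10, 4–9 or 3–8. Without failures the mean difference is 1.44 (below 1.5 because of clipping).

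| Failures, by arm | Mean difference, recorded score | Failed score below completed score | Mann-Whitney power: recorded / ranked worst |
|---|---|---|---|
| 1% v 5% | 1.43 | under 1% of pairs | not run |
| 5% v 14% | 1.36 | 4% | 84% / 85% |
| 16% v 31% | 1.19 | 12.5% | 80% / 80% |
| 25% v 43% | 1.04 | 17% | 76% / 77% |

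The failure rates, mean differences and reversal rates were confirmed by direct summation over the 0–10 scale. Power comes from 10,000 simulated trials per setting (error 0.4 to 0.5 point).

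**4. Size if everyone stops at the same threshold.** Assumed: means 5.0 v 3.5, SD 2.4, 50 per arm, failure at NRS 9, 8 or 7 and above, 4,000 trials each. Here the recorded worst score equals the pain score by construction.

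| Failures, FIC / PENG | Recorded score: difference, power | Failures excluded: difference, power |
|---|---|---|
| 7% / 2% | 1.44, 86% | 1.20, 78% |
| 15% / 5% | 1.43, 85% | 1.03, 68% |
| 26% / 10% | 1.43, 86% | 0.86, 55% |

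The recorded score loses nothing here, so the dilution in step 3 comes from the assumed tolerance model and not from failure as such.

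**5. Type I error.** Setup of step 3 with both means at 4.75, giving failure rates of 9%, 23% and 34% in each arm.

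- Recorded score alone: 5.3%, 4.8%, 4.8%.
- Smaller P of recorded and ranked-worst: 5.9%, 6.7%, 7.8%, an increase of 0.6, 1.9 and 3.0 points.
- Smallest P with exclusion as a third option: 7.9%, 8.9%, 10.3%.
- With rare failures (separate run of 4,000 trials): 4.6% for the recorded score, 4.7% for the best of two, 5.8% for the best of three.

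Any one rule applied consistently holds the nominal level or close to it. The increase appears only when the analyst selects on P.

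**The case for a change.** The best case for a change is that a natural reading is still not a written rule. The trialists foresaw failures and chose to record them separately, so an analyst could read the flag as meaning that the test was not done and drop the case. Exclusion would be damaging: power falls to 78%, 68% and 55% in step 4, and a separate 4,000-trial run of the step 3 model gave 72%, 60% and 49%. Even the two rules that keep everyone disagree on P < 0.05 in 2%, 9% and 17% of simulated trials across the three main step 3 settings. A sentence would cost almost nothing.

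The wording gap stands, and so does the harm from exclusion. But exclusion means discarding a score that the protocol expressly has collected for these very participants, which makes it the least plausible reading. Ranking failures worst has no support in the text either, gains no material power, and does not estimate the NRS difference on which the sample size rests. The sentence would only record what a competent analyst would do anyway.

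The dilution argument does not support a change of analysis. The 1.5 points are attached to the NRS score in general, not to pain on completed rotation. Reporting the proportion unable to rotate would reveal dilution without correcting it, and its test would be weak at 50 per group (χ² power 31%, 44% and 48% in the three main step 3 settings). It is useful description, and the categorical tests already in the plan allow it.

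**Conclusion.** No change is needed. The plan leaves a detail unstated, and the rest of the document supplies it: the worst NRS during the attempts is the 30-minute rotation score, and nobody is dropped. Followed that way, the primary rotation comparison is sound. Power is about 84%, 80% and 76% under variable tolerance and 85% to 86% under a common threshold, with type I error near 5%.

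Two effects remain conditional. Type I error rises only if the rule is chosen by its result. The difference falls materially, to 1.04 against 1.44 points in the most extreme setting, only if failures are frequent, unequal and scored at a personal tolerance below full-rotation pain. The documents give no failure rate, so all these sizes rest on assumed ones; with rare failures both effects are small or negligible. Confidence is moderate, because the conclusion depends on analysts taking the natural reading.

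### Two primary pain scores (at rest and on passive rotation) have no decision rule; if either one suffices, the false-positive rate is about 7% to 9.75% rather than 5%

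*Combined protocol and SAP*

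**What the plan says.** The Outcome measurements section defines the primary outcome in one sentence: "The primary outcome of this study is the pain measurement at rest and during the fractured limb being passively internally rotated", at 30 minutes after the block.

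The Methods section shows that these are two measurements. Assessors record "pain at rest and during the fractured lower limb being passively internal rotated in extension to neutral position", each on the 0–10 NRS. Rotation also has its own recording rule for patients who cannot tolerate it: "impossibility to perform the test will be recorded as well as the worst NRS score during these attempts". No sum, mean or maximum of the two scores is defined.

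The Statistics section gives one calculation, from an SD of 2.4 and a difference of 1.5 NRS points, without saying whether these refer to rest or to rotation: "44 patients in each group are required to achieve a power of 80% and a level of significance of 5% (two sided"). It then plans that "One hundred eligible patients (50 patients in each group) will be enrolled in the study". The tests are the independent t-test or, if the data are not normal, the Mann-Whitney U test. A P value below 0.05 "will be considered statistically significant". There is no either/both rule, no order of testing and no division of alpha. The document is both protocol and SAP and points to no further plan.

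**The concern.** With two primary scores and one threshold, the plan does not define a positive trial. Followed as written, each score can be called significant at an unadjusted 5%.

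- If either score can establish superiority, the overall false-positive rate exceeds the stated 5%.
- If both must be significant, the 5% level holds, but the power of the trial is that of two tests passing together, whereas the sample size was set for one.

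The practical risk is a split result, with one score significant and the other not. The same data could then be reported as a success or a failure, and nothing in the plan prevents that choice from being made after the results are known.

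**Working it through.** **Inputs.** From the Statistics section: SD 2.4, difference 1.5, two-sided alpha 0.05, power 80%, 44 per group required, 50 per group enrolled. Assumed, because the documents do not give it: a correlation r between the two scores of 0 to 0.9. SD 2.4 is taken for both scores.

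**1. The plan's own figure.** The standardised difference is 1.5/2.4 = 0.625.

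- Normal approximation: n = 2 × [2.4 × (1.960 + 0.842)/1.5]² = 40.2, so 41 per group.
- Exact noncentral t: 42 per group (power 80.8%).
- Mann-Whitney efficiency 3/π ≈ 0.955: 42/0.955 = 43.98, so 44 per group.

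The stated 44 therefore matches a single comparison. Exact t-test power for one score is 82.6% at 44 per group and 87.2% at 50.

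**2. Either score suffices, no true difference on either.** For independent scores the error is 1 − 0.95² = 0.0975. For correlated scores it is P(|Z₁| > 1.96 or |Z₂| > 1.96) under a bivariate normal distribution. Simulated t-tests at 50 per group agree, and simulated Mann-Whitney tests give almost the same (9.8% at r = 0, 7.0% at r = 0.9).

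**3. Both scores required, true difference 1.5 on each.** At r = 0, power is the single-test power squared: 0.826² = 0.68 at 44 per group and 0.872² = 0.76 at 50. Other correlations come from at least 1,000,000 simulated trials per setting.

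**4. Split results.** With equal effects on both scores, P(exactly one significant) = 2 × (single-test power − power for both). At 50 per group and r = 0.9 this is 2 × (0.872 − 0.834) ≈ 0.075.

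| r | Error, either rule | Power, both rule, 44/group | Power, both rule, 50/group | Exactly one significant, 50/group |
|---|---|---|---|---|
| 0 | 9.75% | 68.3% | 76.0% | 22.4% |
| 0.5 | 9.1% | 72.3% | 78.9% | 16.5% |
| 0.7 | 8.4% | 74.5% | 80.7% | 13% |
| 0.9 | 7.0% | 78.0% | 83.4% | 7.5% |

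Power columns are for the t-test. At 50 per group the both rule reaches 80% from r of about 0.65. By Mann-Whitney (40,000 simulated trials per setting), power under the both rule is 65% to 76% at 44 per group and 73% to 81% at 50.

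If the 1.5-point difference exists on one score and none on the other, exactly one score is significant in 84% to 87% of trials at 50 per group.

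**5. Power under the repairs (t-test).** A first-ranked score tested at 5% keeps 82.6% at 44 and 87.2% at 50 per group (80.8% and 85.6% by Mann-Whitney). At the 2.5% first step of Holm, one score has 74.1% at 44 and 80.0% at 50 (about 72% and 78% by Mann-Whitney). These are lower bounds for Holm: with 1.5 on both scores, its power per score is about 78% to 80% at 44 and 83% to 86% at 50.

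**The case against.** The strongest reply is that the two scores are joined by the word *and* under a singular primary outcome, so requiring both is at least as natural a reading, and under it the error rate is not inflated. It is true that the text does not state an either rule, and the inflation is conditional on that reading. But in this sentence the conjunction lists what is measured; it does not set a criterion for success. If both were meant, 44 per group would not give the stated 80% power at any correlation from 0 to 0.9.

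Three further points have some force.

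- The 7% figure depends on stopping at a correlation of 0.9: the error is 6.5% at 0.95 and 5.7% at 0.99. It approaches 5% only if the scores are nearly identical.
- The planned 50 per group largely absorbs the power loss under the both rule, if data are complete and the t-test is used. No loss rate is given. As an illustration, with 47 per group evaluable, 80% would be reached only from a correlation of about 0.85. The primary scores are taken before surgery, so losses may be small.
- The 84% to 87% figure for split results assumes the full effect on one score and none on the other. The documents neither predict nor exclude that pattern.

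These points limit the size of the problem. None supplies the missing rule.

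**Conclusion.** The concern holds. The plan names two primary scores, sizes one comparison, and does not say what counts as success.

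If either score suffices, the error rate is 9.75% for independent scores and about 7% at a correlation of 0.9. This assumes no true difference on either score and counts significance in either direction. If both are required, error is controlled, and the t-test power is 68% to 78% at 44 per group and 76% to 83% at 50 with complete data, assuming SD 2.4 and a difference of 1.5 on both scores.

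The point needs fixing because it governs the trial's main conclusion: even with equal true effects on both scores, about 8% to 22% of trials of 50 per group would give a split result that the plan cannot interpret.

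**What to change.** Before any comparative data are seen, rank the two scores and test them in fixed sequence. Possible wording:

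> The primary outcome is NRS pain on passive internal rotation at 30 min, tested at two-sided 5%. NRS pain at rest at 30 min is tested next, at two-sided 5%, only if the first test is significant; otherwise it is reported descriptively. The SD of 2.4 and the difference of 1.5 refer to the first-ranked score.

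Which score comes first is for the investigators to decide. If 2.4 or 1.5 does not apply to that score, the sample size should be recalculated.

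Alternatives are to keep both scores with Holm's procedure, or to state that both must be significant. Either would also settle the rule, and the power should then be restated.

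The cost is two or three sentences in Outcome measurements and Statistics, with no extra patients or data. Under fixed sequence the second-ranked score depends on the first. If its true difference is also 1.5, its t-test power at 50 per group is about 76% to 83% instead of 87%.
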